## 1.0 Objectives / Specific Aims

The objective of this pilot project is to assess the impact of the novel sensory vibration stimulation technique we have developed, named TheraBracelet, in enhancing outcomes of constraint-induced movement therapy (CIMT) in children with cerebral palsy (CP).

TheraBracelet is peripheral sensory stimulation involving application of low-level (imperceptible), random-frequency vibration to the wrist skin. The hypothesis is that improvement in upper extremity function will be greater for the experimental group receiving the TheraBracelet stimulation during CIMT compared with the control group who will wear the device with no vibration (placebo).

## 2.0 Background

Pediatric CIMT is one of the most effective treatment approaches for children with unilateral motor weakness or hemiparesis, regardless of the neuromotor impairment's etiology (Ramey et al. 2013). CIMT involves applying a hand splint and mitt on the stronger, unaffected upper extremity a hand splint and mitt on the stronger upper extremity to encourage use of the affected upper limb in intensive therapy. Research evidence supports the use of intensive therapy models, such as CIMT, to improve overall function in adults and children with one-sided motor weakness or a hemiparesis (Taub et al. 2007 & 2004, Eliasson et al. 2005, Brady and Garcia 2009, Case-Smith et al. 2012, Huang et al. 2009, Coker et al. 2009, DeLuca et al. 2003, 2007, 2012a,b, Nelles 2004, Sakzewski et al. 2009, Al-Oraibi and Eliasson 2011, Barry 2001, Bower and McClellan 2004).

[name], OTR, FAOTA co-developed and currently hold a yearly one-week modified pediatric CIMT camp at MUSC which has provided an intensive CIMT therapy program for over 200 children (approximately 3 to 9 years of age) with hemiplegic CP since 2001 and is an ongoing annual effort. The camp provides a hands-on learning opportunity for occupational and physical therapy students who serve as camp counselors under the mentorship of licensed therapists. The intensive group-based day camp program is now embedded into the occupational and physical therapy course curriculum and a systematic course with training modules has been developed to teach students how to provide the essential components of pediatric CIMT. The children that have participated in this intensive 30 hour CIMT program have demonstrated significant improvements in overall self-care, upper extremity function and mobility skills (Coker et al 2010, Ramey et al 2013).

## 3.0 Intervention to be studied

TheraBracelet stimulation entails application of low-level, random-frequency vibration to the wrist skin, to affect the cortical sensorimotor activity during concurrent upper extremity activities, with an intent to increase outcomes of therapy. Unlike existing methods including transcutaneous electrical nerve stimulation, muscle/tendon vibration, and repetitive transcranial

magnetic stimulation that require prior exposure to the sensory stimulation as long as 2 hours before each therapy session, TheraBracelet can immediately and continuously prime the central sensorimotor system based on preliminary data using neuroimaging (in preparation), and enhance hand motor scores (as measured by the Box and Block and Nine Hole Peg Tests) (Seo et al. 2014) and finger sensory scores (as measured by the Semmes-Weinstein Monofilament Test) (Enders et al. 2013) in adult stroke survivors while TheraBracelet was on. TheraBracelet stimulation is given to the wrist so that the entire hand is exposed to receive relevant sensory information and appropriately manipulate objects. Wearable wrist devices with a vibrating function are low cost and can be easily adopted for rehabilitation purposes to impact a wide range of patients with sensorimotor impairment. TheraBracelet has been used concurrently during 2-week therapy in adults with stroke and resulted in significantly greater improvement in the hand dexterity score compared to dose-matched therapy with no TheraBracelet, in the PI's previous study (in review).

Device: TheraBracelet stimulation is provided by a vibrator connected to an MP3-playing watch via an audio jack (see the pictures below; total weight 40g, watch=3.7cm×5.3cm). No external power source is needed, since the MP3 player drives the vibrator with its internal battery. Both the vibrator and watch are off-the-shelf products (i.e. available to purchase for anyone). The MP3 player/watch is charged using a conventional phone charger. The MP3 player can play any file including the treatment vibration file with white noise vibratory signal and control file with zero amplitude (i.e. no vibration). The treatment vibration will be scaled to a level that is 40% below the sensory threshold for healthy adults without neurologic disorders, neuropathy, or compromised skin (i.e., the treatment vibration is imperceptible to healthy adults). The rationale for the subthreshold intensity is that our previous studies with TheraBracelet showed that this level of imperceptible vibration intensity improved finger sensation more than suprathreshold (i.e., perceptible) vibration in healthy adults as well as adult stroke survivors. Adults' sensory threshold will be used, as children could not reliably respond regarding their perception of barely noticeable or unnoticeable vibration.

FDA: The use of the vibrator for this proposed purpose of affecting the cortical sensorimotor activity during therapy with an intent to increase therapy outcomes has not been approved by the FDA. The vibrator is a general-purpose vibrator, not specifically designed for any particular purpose.

Safety: Currently there is no vibration exposure guideline for this small level of vibration (at 40% below the sensory threshold). People are exposed to higher-intensity, suprathreshold

vibration daily (e.g. from a phone, riding a car). Truck drivers who get exposed to whole-body vibration are limited to driving 11 hours after 10 consecutive hours off duty, according to Federal Motor Carrier Safety Administration. TheraBracelet has been used during 2-week therapy (2 hours/session, 3 sessions/week for 2 weeks) in adults with stroke and resulted in significantly greater improvement in the hand dexterity score compared to dose-matched therapy with no TheraBracelet, without adverse events (i.e., no skin irritation, no numbness) in the PI's previous study (in review). In the PI's current study, TheraBracelet is being used all day (during waking hours), everyday, for a month, in adult stroke survivors, without a safety concern thus far. TheraBracelet has not been used in children, although high-level (i.e. perceivable) vibration has been used in children with CP to treat spasticity and motor function (Katusic et al. 2013).

Control/placebo: No vibration will be the control condition. The MP3 player will play a zero-amplitude file, producing no vibration.

#### **4.0 Inclusion and Exclusion Criteria / Study Population**

Children will be between the ages of 3 and 9 year of age and have a unilateral upper limb motor weakness. The child must use the affected extremity as a gross assist during play and self-care activities. The children demonstrate no significant developmental delays that would limit spontaneous use of the more affected extremity. The children will be ambulatory for their age and demonstrate intact balance and protective reactions throughout the less involved upper extremity. The children will have no other health impairment other than hemiparesis. No inclusion or exclusion criteria will be based on race or gender.

#### **5.0 Number of Subjects**

Total Planned Enrollment: 20

#### **6.0 Setting**

Site: Laboratories of the College of Health Professions, [name]  
The camp will be directed by [name] who is a licensed occupational therapist and will be staffed with a physical therapist and camp counselors. The camp counselors will be occupational and physical therapy students enrolled in programs at the Medical University of South Carolina. This will allow each camper to have 2-to-1 ratio of staff to child ratio with personnel that have experience working with children.

#### **7.0 Recruitment Methods**

Participants for this study will be recruited children who attend the yearly camp CIMT program. Parents/guardians of all children who will attend the CIMT program will be informed of the study. The CIMT is an ongoing yearly camp.

#### **8.0 Consent Process**

Study personnel will obtain the informed consent of the parent, parent/guardian, or guardian of each child participating in the study. In a private setting, the content of the consent will be verbally explained and the parent/guardian will be asked to raise any questions and concerns. If the person requests a waiting period, then one will be given. If the person desires to consent immediately, then the person will provide consent immediately.

## **9.0 Study Design / Methods**

Study design: The study will be a double-blinded stratified randomized controlled trial. Consented children will be stratified in terms of their functional levels (based on MACS). Within each functional level, children will be randomly assigned to either the experimental or control group, in a balanced manner (half the children assigned to one group, and the other half assigned to the other group). All consented children will receive CIMT 6 hours/day, 5 consecutive days for 1 week. This duration of CIMT resulted in significant improvement in capacity and quality of affected upper limb functioning (Coker et al 2010, Ramey et al 2013, Coker-Bolt et al 2017). All consented children will wear the TheraBracelet device during CIMT. The device will provide treatment vibration to the experimental group and no vibration to the control group.

Blinding: A custom MATLAB program will perform group assignment and produce a treatment vibration or zero vibration file depending on the group assignment for each child. The produced vibration file will be uploaded to the TheraBracelet device for each child, and used throughout CIMT. The treatment vibration is imperceptible to healthy adults. Therefore, all personnel involved in CIMT will be blinded to the group assignment. It is anticipated that children who receive treatment vibration would not perceive the vibration from the TheraBracelet device. In an unanticipated case where a child indicates that s/he perceives vibration any time during CIMT, the vibration intensity will be lowered immediately.

Pediatric CIMT protocol: 1) The soft mitt will be worn on the child's stronger, less affected upper extremity during CIMT. 2) The child will be engaged fun, playful camp-based activities to encourage repetitive practice with the weaker limb and shaping of more mature motor responses while the mitt is being worn. These play activities will be implemented by MUSC occupational and physical therapy students who are supervised by licensed therapists. 3) Tasks such as reaching, grasping, and manipulation of objects, weight-bearing, and making hand gestures with the weaker limb will be encouraged during play activities. 4) When the children demonstrate new motor movements, students and therapists will shape and guide the quality of these movements through participation in age appropriate activities.

Outcome Measures: Experimental and control groups will be compared for post-therapy changes in the upper limb functioning. The upper limb functioning in daily living will be measured by standard pediatric therapy parent's questionnaire assessments before and after therapy. The quality and quantity of upper limb movements will be measured by the Quality of Upper Extremity Skills Test, and the Box and Block and Nine-Hole Peg Tests, respectively. Additionally, goal attainment scaling will be used to measure achievements of goals after CIMT. Lastly, we will measure the wear time of the device and the child pain level at each CIMT day.

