## **10.0 Data Management**

Confidentiality protection: The data from test results will be de-identified once it has been collected and before it is stored. This means individual results would not be able to be linked to the participant by others who review the results of this research. The linkage between participant codes and identities as well as all other identifiable information including consent forms will be stored in a locked room and be accessible only to the study personnel.

Analysis: Repeated measures ANOVA with post hoc comparisons will be used to determine if each clinical hand function score improves more for the experimental compared with the control group. A significant interaction between time (pre/post) and group (experimental/control) will support the hypothesis that improvement of upper limb function will be greater with the low-level vibration stimulation.

Sample size determination: This is a pilot study using a convenience sample of children who will attend the summer CIMT camp program at MUSC.

Data sharing: Only de-identified coded data will be reported and/or shared with the public in publications, in ClinicalTrials.gov, or upon written request.

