## **11.0 Provisions to Monitor the Data to Ensure the Safety of Subjects**

Data and Safety Monitoring Board (DSMB): The primary purpose of the DSMB is to ensure the safety of participants and the validity and integrity of data collected during the study. By having the DSMB, safety concerns will be assessed and addressed objectively. If the intervention definitively has safety concerns, the DSMB may make recommendations to address the safety concerns.

The DSMB will be composed of (1) a board certified physician with expertise in neurologic disorders, (2) a registered and licensed occupational therapist with expertise in rehabilitation, and (3) a biostatistician with expertise in design and analysis of clinical trials.

The responsibilities of the DSMB are as follows. Prior to enrollment, the DSMB will review the study design, protocol, recruitment/enrollment plan, statistical analysis plan, and data safety monitoring plan, and document the agreement or recommendation. After enrollment begins and the CIMT camp is provided, the DSMB will convene again to review the safety data, enrollment data including any discontinuation of participation in the study with or without adverse events, and study results. Safety data will include emergence of skin irritation, increase in muscle tone, reduction in the number of functional tasks completed by children, worsening in the quality of motor movements in children, and any other adverse events noted by camp counselors and/or licensed therapists, regardless of whether it is related to the device use or not. The DSMB will review the aggregated summary data as well as the individual participants' data (de-identified). The DSMB will have access to coded (de-identified) data but not identifiable data. The group

assignment information will become available upon completion of the data collection. The DSMB will provide recommendations for adverse events and safety concerns. The DSMB will also provide a report to the IRB to summarize oversight activities, recommendations, and any concerns regarding participant safety.

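### Randomisation is balanced within MACS level, but the planned time by group test has no MACS term; if MACS predicts change, the test is conservative and less powerful than a MACS-adjusted one

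*Combined protocol and SAP*

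**What the plan says.** Section 9.0 (Study design) sets up stratified randomisation: "Consented children will be stratified in terms of their functional levels (based on MACS". It continues: "Within each functional level, children will be randomly assigned to either the experimental or control group, in a balanced manner", with half of each level going to each arm. It does not give the number of levels, their expected sizes, or how an odd-sized level is handled.

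Section 10.0 (Analysis) gives the only analysis: "Repeated measures ANOVA with post hoc comparisons will be used to determine if each clinical hand function score improves more". The decision rule is: "A significant interaction between time (pre/post) and group (experimental/control) will support the hypothesis that improvement of upper limb function will be greater". No MACS, stratum or other covariate term is named there or elsewhere. The text does not exclude one.

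Section 5.0 states "Total Planned Enrollment: 20", and section 10.0 explains the number: "This is a pilot study using a convenience sample of children". No significance level, power, effect size or standard deviation is stated.

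**The concern.** The factor used to balance the arms is left out of the model that compares them. Stable differences in ability between MACS levels do no harm, because they cancel when each child's pre score is subtracted from the post score. What matters is whether MACS predicts how much a child changes.

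If it does, balanced allocation puts the same mix of good and poor responders in each arm, so the arm difference is more precise than under simple randomisation. The planned model does not know this. It counts the between-level variation in change as error, and the standard error comes out too large. With only 20 children, a real effect could be missed more often than necessary. Section 10.0 makes a significant interaction the evidence for the hypothesis, so this matters even in a pilot.

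**Working it through.** The plan states no power or error figure, so there is none to reproduce.

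**Inputs from the documents.** N = 20 (section 5.0); half of each MACS level to each arm (section 9.0); a time by group test with two time points and no MACS term (section 10.0).

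**Assumptions, because the documents give no values.** 10 children per arm; two-sided 5%; SD of change = 1; true effect 1 SD unless stated; MACS acts linearly on change and explains a share R² of its variance; stratum sizes 10/10, 6/8/6 or 5/7/5/3.

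**Step 1: what the planned test is.** With two time points, the interaction F equals t² from a two-sample t-test on change, with 20 − 2 = 18 df. A numerical example gave 0.2016 both ways.

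**Step 2: the standard error, strata evenly split.**
- True variance of the arm difference: (2/10)(1 − R²), because the stratum part cancels between arms.
- Expected planned error variance: [18(1 − R²) + 20R²]/18 = 1 + R²/9, because the stratum part stays in the residual.
- Ratio of planned to true standard error: √[(1 + R²/9)/(1 − R²)].
- R² = 0.1: √(1.0111/0.9) = 1.06. R² = 0.2: √(1.0222/0.8) = 1.13. R² = 0.3: √(1.0333/0.7) = 1.21.

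Simulation with 6/8/6 gave 1.063, 1.131 and 1.214.

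**Step 3: error rate and power by simulation** (100,000 runs per setting, effect 1 SD for power).

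| Strata | R² | Type I, planned | Power, planned | Power, additive MACS |
|---|---|---|---|---|
| 10/10 | 0 | .050 | .564 | .561 |
| 10/10 | .05 | .044 | .559 | .579 |
| 10/10 | .1 | .038 | .560 | .604 |
| 10/10 | .2 | .029 | .558 | .654 |
| 10/10 | .3 | .019 | .556 | .712 |
| 6/8/6 | 0 | .049 | .565 | .560 |
| 6/8/6 | .05 | .044 | .565 | .582 |
| 6/8/6 | .1 | .039 | .558 | .599 |
| 6/8/6 | .2 | .029 | .558 | .650 |
| 6/8/6 | .3 | .019 | .556 | .709 |
| 5/7/5/3 | 0 | .049 | .560 | .536 |
| 5/7/5/3 | .05 | .046 | .556 | .554 |
| 5/7/5/3 | .1 | .042 | .555 | .575 |
| 5/7/5/3 | .2 | .032 | .552 | .627 |
| 5/7/5/3 | .3 | .025 | .551 | .684 |

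With additive MACS the type I error was .049 to .051 throughout. The mean estimate was 0.998 to 1.002 in every setting, so there is no bias either way.

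**Step 4: formula check for three evenly split strata.** Adjusted power comes from the noncentral t with 20 − 3 − 1 = 16 df and noncentrality 1/√[0.2(1 − R²)], which is 2.236, 2.357, 2.500 and 2.673 at R² = 0, 0.1, 0.2 and 0.3. This gives .556, .600, .651 and .709, matching the 6/8/6 rows within simulation error.

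**Step 5: the source of the conservatism.** Under simple randomisation at R² = 0.3, the same unadjusted test has type I error 0.051. The deficit therefore comes from balancing within strata and then ignoring them.

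**Step 6: other effect sizes (6/8/6), planned vs additive power at R² = 0.1, 0.2, 0.3.**
- 0.5 SD: .169 vs .198, .151 vs .213, .135 vs .240.
- 0.8 SD: .383 vs .423, .379 vs .471, .364 vs .525.
- 1.2 SD: .726 vs .760, .732 vs .805, .739 vs .855.

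**Step 7: which MACS term.** In one simulated 6/8/6 data set, the interaction standard error was .4123 with no MACS term and .4123 with a MACS main effect alone. It was .3447 with MACS by time, identical to a change-score model with stratum, and .3704 with the fully crossed model. With 5/7/5/3 the fully crossed model has power .479 at R² = 0 and .515 at R² = 0.1, below the planned test's .560 and .555.

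**The case against.** The strongest reply is that nothing is broken. False positives are not inflated, the estimate is unbiased, this is a pilot with no power target, and section 10.0 leaves a MACS term unmentioned rather than excluding it. All of that stands, and it limits the point to a recommended improvement.

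Second, the gain depends on quantities the documents do not give. Section 4.0 restricts the population (some functional use of the affected limb, walking as expected for age), which may narrow the MACS range. With very sparse levels (1/3/9/7 or 1/5/7/5/2) a categorical term gives power of 0.53 to 0.55 against 0.56 at R² = 0.05, and is about even at R² = 0.1. This also stands. A one-df ordinal MACS term did better in those layouts (0.57 to 0.58 at R² = 0.05, 0.59 to 0.60 at R² = 0.1), although the simulated MACS effect was linear, which favours it.

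Third, losing power needs a comparator. For a 1-SD effect the planned power hardly moves with R² (.565 to .556 with 6/8/6). The loss is relative to the MACS-adjusted test, and it is stated that way here.

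None of this removes the mismatch between allocation and analysis, or the asymmetry between a small cost and a possibly larger gain.

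**Conclusion.** The concern holds, conditionally: if MACS predicts pre-to-post change, the planned test is conservative and less powerful than one that includes the stratum. At 1 SD and across the three assumed layouts, the power forgone is about 2 to 4 points at R² = 0.1, 7 to 10 at R² = 0.2 and 13 to 16 at R² = 0.3. At R² = 0.05 the gain is about 2 points (10/10, 6/8/6) or nil (5/7/5/3). If MACS is unrelated to change, adding it costs 0.3, 0.5 or 2.4 points (10/10, 6/8/6, 5/7/5/3).

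These sizes rest on assumed strata, R² and effect; the direction does not. The planned test is valid and no stated figure is overturned. The change should be made because it is cheap and uses the factor the trial already chose to balance.

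**What to change.** Add to section 10.0:

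> For each score measured before and after CIMT, the between-group test includes the MACS stratum used in randomisation additively: MACS and MACS × time in the repeated measures ANOVA, with no group × MACS × time term, or equivalently a stratum factor in the change-score model (or in a baseline-adjusted ANCOVA, if one is used). For a score measured only after CIMT, the stratum is a factor in the group comparison. Any stratum with fewer than two children at randomisation is pooled with the adjacent MACS level (the smaller neighbour if there are two; the lower-numbered level if these are equal), decided on stratum size alone, without reference to allocation or outcome data.

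The clause on scores taken only after camp is needed because "goal attainment scaling will be used to measure achievements of goals after CIMT"; if that measure has no pre value, a time by group test cannot be applied to it. The pooling rule is needed because a single-child stratum adds nothing to the adjusted contrast. With 1/9/9/1 at R² = 0, power is .505 unpooled and .550 pooled, against .556 as planned. If very sparse levels are expected, a one-df ordinal MACS term could be specified in advance instead.

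The cost is wording. MACS is already recorded for randomisation. The term uses 1, 2 or 3 residual df with two, three or four strata. If MACS does not predict change, power falls by about 0 to 3 points in the change-score model, or 1 to 4 points on top of a baseline adjustment. The text should be settled while allocation is blinded; section 11.0 says "assignment information will become available upon completion of the data collection". That also prevents a later choice between adjusted and unadjusted results.

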## **12.0Risks to Subjects**

- Confidentiality: There is a risk for loss of confidentiality.
- Injury: There is a risk for injury during engagement in play activities involved in therapy interventions. Although therapy interventions used in the pediatric CIMT involve those play activities that a child would normally engage in during a typical day, children are at risk for injury during play and daily activities. There is a risk of physical and mental fatigue from engaging in the CIMT.
- Mitt restraint: There is a risk of skin breakdown or irritation from the soft mitt restraint and stiffness in the less involved limb being constrained. The children could become frustrated or anxious from having their stronger hand restrained for several hours a day.
- Randomization: The treatment a person receives may prove to be less effective or to have more side effects than the other study treatment or other available treatments.
- Watch/Vibration: There is a minor risk of skin irritation from wearing the wristband and/or from vibration. There is a minor risk of discomfort in moving the arm/hand due to the weight of the device on the wrist, although the device weighs only 40g. Potential risks that may be associated with prolonged use of wrist vibration, including irritation, muscle tones, reduction in the number of functional tasks completed by children, and worsening in the quality of motor movements in children will be noted during each day of CIMT, and formally assessed during pre/post assessments.
- There is also a risk of unexpected medical emergencies.

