## **13.0 Potential Benefits to Subjects or Others**

There may be no benefit from participating in this study. The potential benefit is that the vibration the person receives may help their upper extremity functional recovery, although this

cannot be guaranteed. The knowledge regarding the potential of using low-level vibration as a therapy adjunct is important to increase functional recovery of children with CP and may benefit those with CP in general. The risks are deemed reasonable in relation to the potential gain of knowledge regarding TheraBracelet's feasibility, safety, and efficacy in potentially enhancing upper extremity function.

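### Does the plan need to list a child's report of felt vibration, and the resulting intensity change, as recorded data?

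*Combined protocol and SAP*

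**What the plan says.** Section 3.0 (Device) sets the treatment vibration 40% below the sensory threshold of healthy adults. It uses adults because children are judged unable to say reliably whether they feel a barely noticeable vibration. On the control device, "The MP3 player will play a zero-amplitude file, producing no vibration".

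Section 9.0 (Blinding) has each child's file loaded on the device for the whole camp. It then says: "It is anticipated that children who receive treatment vibration would not perceive the vibration from the TheraBracelet device". The exception follows at once: "In an unanticipated case where a child indicates that s/he perceives vibration any time during CIMT, the vibration intensity will be lowered immediately".

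Three places say what is recorded during the camp:

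- Section 9.0 (Outcome Measures), after the function tests, parent questionnaires and goal attainment: "we will measure the wear time of the device and the child pain level at each CIMT day".
- Section 11.0, for the DSMB: "Safety data will include emergence of skin irritation, increase in muscle tone, reduction in the number of functional tasks completed by children". It goes on to worsening movement quality, any other adverse events, discontinuations and study results.
- Section 12.0 (Watch/Vibration): similar signs, which "will be noted during each day of CIMT, and formally assessed during pre/post assessments".

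None of these names a report of felt vibration or a change of intensity. Section 10.0 tests the time-by-group interaction in a repeated measures ANOVA and does not use delivered intensity.

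**The concern.** The lowering rule is the only place where the plan alters the randomised intervention while it is being given, and no recording step is attached to it. Wear time is the only exposure measure, and it carries no information on intensity. A treated child whose setting was lowered on day 2 could finish the week with complete wear time and nothing in the required record to show the change.

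Two things would then be at stake. If the groups did not differ, the team could not tell an ineffective treatment from one delivered at a different setting. And the pilot could not report how often children in either arm said they felt something. That second loss seems awkward because "TheraBracelet has not been used in children", and because Section 13.0 counts among the knowledge to be gained the device's "feasibility, safety, and efficacy in potentially enhancing upper extremity function". Once a one-week camp is over, the information is hard to reconstruct.

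**Working it through.** The protocol gives no figure on this point to reproduce; the sample of 20 is a convenience sample (Section 10.0).

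**Inputs.** Planned enrolment is 20 (Section 5.0), split in half within functional level (Section 9.0), so about 10 per arm. Camp exposure is 6 h × 5 days = 30 h per child (Section 9.0). The protocol gives no rate of reports and no size of intensity step.

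**1. Hours at a changed setting.** If the setting is lowered at the start of day d, the hours affected are 6 × (6 − d). For d = 1 to 5 this gives 30, 24, 18, 12 and 6 of 30 h. Wear time reads 30 h in every case, and that is right: the device was worn. What is unlisted is the setting.

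**2. Largest dilution per affected child.** Assume the lowered setting has no effect at all and that benefit is proportional to hours. One treated child among 10 then reduces the estimated group difference by [(6 − d)/5] ÷ 10, which is 10%, 8%, 6%, 4% or 2% for d = 1 to 5. If 1, 2 or 3 treated children were lowered from day 2, the affected hours would be 24, 48 or 72 of the arm's 10 × 30 = 300 h, or 8%, 16% or 24%.

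**3. Is that assumption supported?** The documents do not support it. The intervention is defined as imperceptible vibration, and Section 3.0 reports that, in adults, the imperceptible level improved finger sensation more than a perceptible one. A child who truly feels the vibration is already outside the intended condition, so lowering may bring exposure nearer to it. The loss could be nil, or its sign could reverse. In the control arm the amplitude is zero, so lowering it changes nothing.

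**4. How likely is any report?** This depends on an unknown rate. If the chance that a treated child reports were 5%, 10%, 20% or 30%, the chance of at least one report among 10 is 1 − (1 − p)^10 = 40%, 65%, 89% or 97%. These rates are assumptions that show the range.

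**5. What would a log show?** With 0 of 10 treated children reporting, the exact (Clopper-Pearson) 95% upper limit is 1 − 0.025^(1/10) = 31%. With 1 of 10 the interval is 0.3% to 45%. These limits apply to the chance that a child aged 3 to 9 volunteers a report. They do not bound the chance that the child perceives the vibration, because Section 3.0 regards such reports as unreliable near threshold. An empty log would therefore not demonstrate imperceptibility.

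**6. Does the planned comparison depend on it?** It does not. The rule is written for any child, not only a treated one, and the personnel running the camp are blinded. The comparison is between children assigned to the vibration regime, lowering rule included, and children assigned to zero amplitude. It is valid whether or not the rule is triggered.

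**The case for a change.** The strongest case for a change is that recording is cheap and possible only prospectively. Two extra fields on a daily record already kept would cover at most 20 × 5 = 100 child-days. Imperceptibility underpins both the treatment concept and the blind, yet for children it is expected rather than measured. The catch-all in Section 11.0 is for adverse events, and feeling a faint vibration need not be one. A first use in children would do well to report such events by arm.

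Much of this stands. The lists do not name the event, the plan does not oblige anyone to write it down, and a note of it in both arms would be useful descriptive information.

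It falls short of requiring a change for four reasons:

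- Demonstrating imperceptibility in children is neither an objective in Section 1.0 nor an outcome in Section 9.0. The mention of feasibility occurs in a paragraph on benefits.
- Fields for yes/no and time would not capture the new setting, so delivered exposure would remain unknown even with the log. With about 10 per arm and no power target, they could not reliably separate a null effect from altered exposure either.
- A short protocol that does not itemise its case report form is weak evidence that nothing would be noted. The Section 11.0 list is introduced as what the safety data will include, the DSMB also sees individual participants' data, and study personnel hand out and collect the devices every day (Section 15.0).
- A report might hint weakly at the arm if treated children reported more often than controls, but that rate is unknown and a log would not undo what camp staff had heard.

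**Conclusion.** The observation is accurate, but it describes missing detail and not a flaw in the design or analysis. It matters only if a child reports vibration, which the plan does not expect. Even then wear time is right and the randomised comparison is unaffected. The possible dilution is at most 2% to 10% per affected treated child, assuming about 10 per arm, effect proportional to hours and no effect at the lowered setting. The documents do not support that last assumption, and the loss may be nil.

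The gap is one that competent study staff would probably fill. If they note a volunteered report, its time and the resulting setting under the child's code, with the setting kept from blinded staff and the outcome tester until data collection ends, the counts can be given by arm as description. They should be read as how often children spoke up, not as proof that the vibration went unfelt.

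One point of wording remains. Section 9.0 says the file is used for the whole of CIMT and, a few lines later, that intensity is lowered on a report. These read naturally as a general rule and its exception, but the two statements should be reconciled as a clerical matter. Nothing here takes a view on whether, or how far, intensity should be lowered.
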